10. LVEF < 50%

11. History of severe hemorrhagic or thromboembolic event in the past 12 months (excluding central venous catheter thrombosis and peripheral deep vein thrombosis).
12. Known inherited predisposition to bleeding or to thrombosis in the opinion of the investigator.
13. Patient with brain metastases that are symptomatic and/or require therapy.
14. Patients who require full-dose anticoagulation (according to local guidelines).
No Vitamin K antagonist and other anticoagulation allowed; LMWH allowed only for prevention not for curative treatment.
15. History of pneumonitis within the last 5 years.
16. Patients who are under judicial protection and patients who are legally institutionalized.
17. Patients unable or unwilling to comply with protocol
18. Previous enrolment in this trial (Part 1 or Part 2).
19. Chronic alcohol or drug abuse or any condition that, in the investigator's opinion, makes them an unreliable trial patient or unlikely to complete the trial.
20. Women who are pregnant, nursing, or who plan to become pregnant in the trial

For PART 2:

1. Known hypersensitivity to the trial drugs or their excipients or risk of allergic or anaphylactic reaction to drug product according to Investigator judgement (e.g. patient with history of anaphylactic reaction or autoimmune disease that is not controlled by nonsteroidal anti-inflammatory drugs (NSAIDs), inhaled corticosteroids, or the equivalent of <= 10 mg/day prednisone).
2. Not more than one CPI based treatment regimen prior to entering study (eg. anti-Programmed Death receptor-1 (PD-1), anti-Programmed Death-1 ligand-1 (PD-L1), anti-PD-L2, or anti-cytotoxic T lymphocyte associated antigen-4 (anti-CTLA-4) antibody). In case of CPIs combination, they need to be approved by the local regulatory agencies; for e.g., Melanoma cohort (Cohort E).
3. Known HIV infection
4. Active hepatitis B virus (HBV) or hepatitis C virus (HCV) infection (exception for patients in HCC cohorts; Cohorts F, G & H).
5. History of severe hypersensitivity reactions to other mAbs.

Proprietary confidential information © 2023 Boehringer Ingelheim International GmbH or one or more of its affiliated companies

6. Immunosuppressive corticosteroid doses (> 10 mg prednisone daily or equivalent) within 4 weeks prior to the first dose of trial medication except for control of cerebral edema in case of recurrent glioblastoma (Cohort D).
7. Current or prior treatment with any systemic anti-cancer therapy (including radiotherapy) either within 28 days or a minimum of 5 half-lives, whichever is shorter before start of treatment.
8. Serious concomitant disease, especially those affecting compliance with trial requirements or which are considered relevant for the evaluation of the endpoints of the trial drug, such as neurologic, psychiatric, infectious disease or active ulcers (gastrointestinal tract, skin) or laboratory abnormality that may increase the risk associated with trial participation or trial drug administration, and in the judgment of the investigator would make the patient inappropriate for entry into the trial.
9. Major injuries and/or surgery or bone fracture within 4 weeks of start of treatment, or planned surgical procedures during the trial period.
10. Patients with personal or family history of QT prolongation and/or long QT syndrome, or prolonged QTcF at baseline (> 480 ms).
11. Significant cardiovascular/cerebrovascular diseases (i.e. uncontrolled hypertension, unstable angina, history of infarction within past 6 months, congestive heart failure > NYHA II).
Uncontrolled hypertension defined as: Blood pressure in rested and relaxed condition \geq 140 mmHg, systolic or \geq 90 mmHg diastolic (with or without medication), measured according to [Appendix 10.2](#).
12. LVEF < 50%
13. History of severe hemorrhagic or thromboembolic event in the past 12 months (excluding central venous catheter thrombosis and peripheral deep vein thrombosis).
14. Known inherited predisposition to bleeding or to thrombosis in the opinion of the investigator.
15. Patient with brain metastases that are symptomatic and/or require therapy.
16. Patients who require full-dose anticoagulation (according to local guidelines). No Vitamin K antagonist and other anticoagulation allowed; LMWH allowed only for prevention not for curative treatment.
17. History of pneumonitis (non-infectious) within the last 5 years
18. Patients who are under judicial protection and patients who are legally institutionalized.

19. Patients unable or unwilling to comply with protocol
20. Previous enrolment in this trial.
21. Chronic alcohol or drug abuse or any condition that, in the investigator's opinion, makes them an unreliable trial patient or unlikely to complete the trial.
22. Women who are pregnant, nursing, or who plan to become pregnant in the trial
23. Symptomatic pleural effusion, pericardial effusion, or ascites
24. Prior treatment with any antiangiogenic treatment (e.g. bevacizumab, cediranib, aflibercept, vandetanib, XL-184, sunitinib, etc) except for prior sorafenib or lenvatinib treatment in 2nd line HCC cohort (Cohort F) and for prior treatment with atezolizumab in combination with bevacizumab in Cohort H.
25. Has received a live vaccine within 30 days prior to the first dose of study drug
26. Patients with known active second malignancy other than non-melanoma skin cancers, non-metastatic prostate cancer, in situ cervical cancer, and ductal or lobular carcinoma in situ of the breast. Patients are not considered to have a currently active malignancy if they have completed anticancer therapy and have been disease free for greater than 2 years prior to screening

Further exclusion criteria:

Exclusion criteria for Glioblastoma cohort:

1. Has tumor primarily localized to the brainstem or spinal cord.
2. Has presence of diffuse leptomeningeal disease or extracranial disease.
3. Is known to have IDH mutant variety of recurrent glioblastoma.
4. Any prior treatment with prolepsosan 20 with carmustine wafer.
5. Any prior treatment with an intracerebral agent.

Exclusion criteria for Melanoma cohort:

1. Uveal or ocular melanoma

Exclusion criteria for HCC cohorts (cohorts F, G & H):

1. Co-infection with HBV and HCV or HBV and hepatitis D virus (HDV)
2. Known fibrolamellar HCC, sarcomatoid HCC, or mixed cholangiocarcinoma and HCC

3. Untreated active Hepatitis B virus (HBV)
4. History of hepatic encephalopathy
5. Participants with untreated or incompletely treated varices with bleeding or high-risk for bleeding
6. Treatment with any HCV anti-viral therapy within 4 weeks prior to Cycle 1 Day 1

3.3.4 Withdrawal of patients from therapy or assessments

Patients may potentially be withdrawn from trial treatment or from the trial as a whole (“withdrawal of consent”) with very different implications, please see [Sections 3.3.4.1](#) and [3.3.4.2](#) below.

Every effort should be made to keep entered patients in the trial: if possible on treatment, or at least to collect important trial data.

Measures to control the withdrawal rate include careful patient selection, appropriate explanation of the trial requirements and procedures prior to patient’s participation, as well as the explanation of the consequences of withdrawal.

The decision to withdraw from trial treatment or from the whole trial as well as the reason must be documented in the patient files and eCRF.

3.3.4.1 Withdrawal from trial treatment

An individual patient is to be withdrawn from trial treatment if:

- The patient wants to withdraw from trial treatment, without the need to justify the decision.
- The patient needs to take concomitant drugs that interfere with the investigational product or other trial medication.
- The patient can no longer be treated with trial medication for other medical reasons (such as surgery, adverse events, other diseases, or pregnancy).
- The patient can no longer be treated with trial drug after a drug related Adverse Event CTCAE Grade 4.
- The patient can no longer be treated with trial drug after a DLT, which did not recover to CTCAE Grade 1 or pre-treatment values within 2 weeks (not applicable for part 2)
- The patient has repeatedly shown to be non-compliant with important trial procedures and, in the opinion of both, the investigator and sponsor representative, is not willing or able to stick to the trial requirements in the future.

Given the patient’s agreement, the patient will undergo the procedures for early treatment discontinuation and follow up as outlined in the [Flow Chart](#) (FC) and [Section 6.2.3](#).

For all patients, the reason for withdrawal from trial treatment (e.g. adverse events) must be recorded in the eCRF. These data will be included in the trial database and reported.

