on the time of occurrence and the severity of the reaction, the investigator may consider administering additional supportive medication, e.g. corticosteroids for re-introduction. Infusion rate and premedication for further treatment cycles should be adapted according to Investigator decision, but adaption of administration scheme need to be agreed with sponsor. If an infusion related reaction is Grade 3 or higher in severity at any point during the study, treatment with ezabenlimab has to be permanently discontinued.

Premedication:

No premedication will be required for BI 836880 IV or ezabenlimab infusion. If a patient expressed sign of infusion reaction at any BI 836880 treatment, a premedication will be considered for all subsequent treatment infusions (dosage and schedule according investigator's decision) comparable to following scheme:

- Acetaminophen/Paracetamol 650 mg - 1000 mg p.o., or equivalent
- Antihistamine p.o. or i.v., equivalent to Diphenhydramine 50 mg i.v.

Drug re-administration criteria after the first cycle has been completed for Part 1:

Before initiating a new treatment cycle the actual health status will be assessed according to [Flow Chart](#) and described in [Section 5.2.5](#). To continue treatment with further cycles, all of the following criteria must be met:

- No uncontrolled hypertension (according to Exclusion-Criterion #9)
- QTcF <=480 ms (according to Exclusion-Criterion #8)
- Acceptable tolerability (in case of an adverse event at the planned start of a treatment cycle patients may continue therapy only after recovery to a level which would allow further therapy; i.e. CTCAE grade 1 or pre-treatment value or considered not clinically significant)

In case one of the above mentioned criteria is not fulfilled the patient should be re-evaluated for up to 2 weeks. Any case of a delay in treatment cycle should be communicated to the Clinical Monitor at Boehringer Ingelheim. The investigator in agreement with the Clinical Monitor will decide about further treatment of individual patient, based on known risk/benefit of BI 836880 and ezabenlimab.

Rescreening is generally not allowed. In individual cases, rescreening can be considered in alliance with the sponsor.

In case of a DLT (drug related AEs CTCAE Grade 3, 4 according to [Table 5.2.6.1: 1](#)), the patient will discontinue treatment.

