Once a DLT has recovered to CTCAE grade 1 or pre-treatment values, the study drugs may be re-started at a lower dose level in case the patients benefit from the study drug after discussion between investigator and Clinical Monitor at Boehringer Ingelheim.

Drug re-administration criteria after the first cycle has been completed in Part 2:

Before initiating a new treatment cycle the current health status of the patient will be assessed according to the [Flow Chart](#).

To continue treatment with further cycles, all of the following criteria must be met:

1. Pre-infusion SBP should be < 160 mmHg and pre-infusion DBP should be < 100 mmHg; study drug administration of both study drugs should be temporarily delayed until BP < 160/100. Please see [Table 10.2.1: 1](#) in [Appendix 10.2.1](#), which describes the guidelines for BP management and study drug administration.
2. QTcF <=480 ms (according to Exclusion-Criterion #8)
3. Echocardiography if clinically indicated (based on investigators judgment) with Left Ventricular Ejection Fraction (LVEF) $\geq 50\%$
4. Acceptable tolerability (in case of an adverse event at the planned start of a treatment cycle patients may continue therapy only after recovery to a level which would allow further therapy in the opinion of investigator).

In case the above mentioned criteria 2, 3, and 4 are not fulfilled, the patient should be re-evaluated as needed. Any case of a delay in treatment cycle should be communicated to the Clinical Monitor at Boehringer Ingelheim. The investigator in agreement with the Clinical Monitor will decide about further treatment of individual patient, based on known risk/benefit of BI 836880 and ezabenlimab.

Dose reduction guidelines

Part 1:

Administration of trial drugs has to be stopped temporarily in case of a DLT (see [Section 5.2.6.1](#)). Patients may continue therapy only after recovery from DLT to at least fulfil retreatment criteria. The future dose of BI 836880 must be a tested dose which is one dose level below the dose received by the patient (Table 4.1.4: 1 and [4.1.4: 2](#) below) Treatment has to be discontinued in case the DLT is not reversible.

Table 4.1.4: 1 Dose reduction recommendations for BI 836880 in Part I

BI 836880 received dose	BI 836880 reduced dose
720 mg	500 mg
500 mg	360 mg
360 mg	Stop BI 836880

In case of AEs (DLTs) that can be definitely characterized as ezabenlimab related, dose can be reduced.

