- For Grade 3 irAEs, ezabenlimab and BI 836880 has to be withheld, and treatment with high-dose corticosteroids (1-2mg/kg/d) is usually warranted. Upon improvement, steroids should be tapered over 4-6 weeks. Non-steroidal immunosuppressives (e.g. infliximab, mycophenolate mofetil) should be considered if no improvement or worsening occurs within the initial 48 to 72 hours. Upon recovery to grade 1 or less, and on corticosteroid \leq 10 mg per day, restarting of ezabenlimab and BI 836880 may be considered for selected irAEs, but caution is advised, in particular in patients with early-onset irAEs. Expert consultancy is recommended prior to restart of therapy.
- Most Grade 4 irAEs warrant permanent discontinuation of ezabenlimab and BI 836880.
- Restart of therapy is commonly possible for endocrine irAEs regardless of grade once stable hormone replacement has been instituted and symptoms have recovered. In case of multiple hormone deficiencies, corticosteroid replacement has to precede thyroid hormone replacement therapy by several days in order to avoid adrenal crisis.
- A dose reduction of BI 836880 may be considered, but is not required for the first occurrence of an endocrine irAE.

In case of prolonged steroid therapy or treatment with immunosuppressive consider the possibility of opportunistic infections and tuberculosis reactivation, administer prophylactic antibiotics where appropriate.

Commonly, referral to experts in the management of organ-specific conditions is highly recommended, especially for irAEs grade 3 or grade 4, or irAEs where management is complex.

Ezabenlimab and BI 836880 should be permanently discontinued for immune related:

- encephalitis, aseptic meningitis, transverse myelitis, or Guillain-Barre syndrome of any grade
- acquired thrombotic thrombocytopenic purpura of any grade
- myocarditis of any grade
- myasthenia gravis, peripheral neuropathy or autonomic neuropathy of grade ≥ 3
- myositis grade 2 with objective findings (see below), any myositis grade ≥ 3
- hepatitis grade ≥ 3 (transaminase >5 times ULN [or >10 times ULN if baseline was $>2.5-5$ times ULN] or total bilirubin >3 times ULN [or >5 times ULN if baseline was $>1.5-3$ times ULN], recurrent hepatitis grade ≥ 2)
- nephritis grade ≥ 3 , persisting grade 2 nephritis unresponsive to initial steroid therapy or worsening, and recurrent nephritis grade ≥ 2
- pneumonitis grade ≥ 3 ,

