- For Grade 1 events, may continue ezabenlimab and BI 836880, but with low threshold to discontinue while monitoring closely for worsening.
- For Grade 2 events, withhold ezabenlimab and BI 836880 until resolution to grade 1 or less, and on corticosteroid ≤ 10 mg per day. Initiate therapy as appropriate per available guidelines.
- For Grade 3 or grade 4 events, permanently discontinue ezabenlimab and BI 836880.

Inflammatory Arthritis

Proprietary confidential information © 2023 Boehringer Ingelheim International GmbH or one or more of its affiliated companies

- For Grade 1 arthritis, ezabenlimab and BI 836880 can be continued. Administer analgetic treatment (acetaminophen, NSAID).
- For Grade 2-4 arthritis, withhold ezabenlimab and BI 836880. Initiate treatment as per available guidelines, care regarding reactivation of tuberculosis/opportunistic infections in case of prolonged immunosuppressive/disease modifying anti-rheumatic drugs DMARD therapy.

Ezabenlimab and BI 836880 may be restarted after consultancy with rheumatology once recovery to grade 1 or less, and on corticosteroid ≤ 10 mg per day.

Myositis

Diagnostic workup should consider the need to also evaluate myocardial involvement.

- For Grade 1 myositis, ezabenlimab and BI 836880 may be continued. Initiate adequate therapy as clinically warranted. In case of elevated CK or muscle weakness, treat as grade 2.
- For Grade 2 myositis, withhold ezabenlimab and BI 836880, discontinue permanently in patients with objective findings (elevated enzymes, abnormal EMG, abnormal muscle MRI or biopsy). Initiate therapy as per available guidelines. Resuming ezabenlimab and BI 836880 may be considered in patients without objective findings, symptoms have resolved to grade 1 or less without any immunosuppressive therapy, and after consultation with rheumatology/neurology.
- For Grade 3 or 4 myositis, permanently discontinue ezabenlimab and BI 836880.
- Ezabenlimab and BI 836880 should be permanently discontinued if there is any evidence of myocardial involvement.

Polymyalgia-like syndrome

- For Grade 1 event, ezabenlimab and BI 836880 can be continued.
- For Grade 2 event, withhold ezabenlimab and BI 836880 and promptly initiate adequate therapy. If no improvement, treat as grade 3.
- For Grade 3 or Grade 4 event, withhold ezabenlimab and BI 836880, promptly initiate adequate therapy. Rheumatology consultancy is highly recommended.

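### Section 3.3.4.1 withdraws every patient after a drug-related Grade 4 adverse event, while Appendix 10.4 (and, for Part 1, Section 4.1.4) permits restart after some of the same events, and nothing says which text governs

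*Protocol*

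**What the plan says.** Section 3.3.4.1 opens its list in mandatory form: "An individual patient is to be withdrawn from trial treatment if". One entry is "The patient can no longer be treated with trial drug after a drug related Adverse Event CTCAE Grade 4". It carries no condition on recovery, type of event or trial part. The next entry, on DLTs, is qualified on two of these: it covers only a DLT "which did not recover to CTCAE Grade 1 or pre-treatment values within 2 weeks (not applicable for part 2").

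Appendix 10.4 gives the general position for immune-related adverse events (irAEs) as "Most Grade 4 irAEs warrant permanent discontinuation of ezabenlimab and BI 836880", and adds "Restart of therapy is commonly possible for endocrine irAEs regardless of grade once stable hormone replacement has been instituted". Its event-specific blocks then state when treatment is withheld and when it may resume. One example is "For Grade 2-4 arthritis, withhold ezabenlimab and BI 836880", followed by a restart condition.

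Section 4.1.4, under the Part 1 re-administration criteria, has a sentence that opens "In case of a DLT (drug related AEs CTCAE Grade 3, 4 according to" and points to the DLT table. That sentence has the patient discontinue. The next paragraph says "Once a DLT has recovered to CTCAE grade 1 or pre-treatment values, the study drugs may be re-started at a lower dose level", subject to patient benefit and discussion with the sponsor's monitor.

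**The concern.** An irAE that the investigator attributes to either study drug is a drug-related adverse event, so at Grade 4 it falls under Section 3.3.4.1 and Appendix 10.4 together. For several event types the first ends treatment and the second leaves restart open. Two sites with the same patient could act differently, each citing the protocol.

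This is an individual stopping rule for severe toxicity and it is still in use. Recruitment ended in December 2021, but Section 1.1 reports 44 patients on treatment in January 2022. Section 4.1.4 lets treatment run to 53 cycles, with case-by-case extension ending no later than 30 April 2025. There is also a small reporting consequence: drug-related adverse events leading to discontinuation are a secondary endpoint, and the count depends partly on which section a site followed.

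**Working it through.** The question is one of text, so the provisions are set side by side. All are current text, not the amendment log.

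**Step 1. Scope of the withdrawal rule.** Section 3.3.4.1 applies to any Grade 4 event judged drug-related, in Part 1 and Part 2. Only the neighbouring DLT entry is switched off for Part 2 and tied to recovery.

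**Step 2. Appendix 10.4 at Grade 4.**

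| Event | Action at Grade 4 | Restart route | Section 3.3.4.1, if drug-related |
|---|---|---|---|
| Endocrine irAEs in general | varies by event | yes, at any grade, on stable replacement and after recovery | withdraw |
| Hyperglycaemia with ketosis (Grade 3-4) | withhold | yes, when insulin gives stable control | withdraw |
| Hypothyroidism (Grade 3-4) | withhold | yes, when symptoms are back to baseline on supplementation | withdraw |
| Hyperthyroidism (Grade 3-4) | withhold | yes, when symptoms are back to baseline | withdraw |
| Adrenal insufficiency (Grade 3 and 4) | interrupt | yes, on stable replacement | withdraw |
| Inflammatory arthritis (Grade 2-4) | withhold | yes, after specialist advice and recovery to Grade 1 or less on low-dose steroid | withdraw |
| Polymyalgia-like syndrome (Grade 3 or 4) | withhold | yes, after benefit-risk assessment and recovery to Grade 1 or less on low-dose steroid | withdraw |

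**Step 3. Where the sections agree.** For Grade 4 pneumonitis, colitis, hepatitis, nephritis, rash, myocarditis and immune thrombocytopenia, among others, Appendix 10.4 also ends treatment. The conflict is confined to the events in the table and, in Part 1, to recovered Grade 4 DLTs.

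**Step 4. Section 4.1.4, Part 1.** The DLT table in Section 5.2.6.1 counts any related Grade 4 non-laboratory event as a DLT, apart from its listed exceptions. Grade 4 events are therefore inside the restart permission, which has no Grade 4 exclusion.

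**Step 5. Precedence.** None of the three texts cites another as an exception or as overriding, and none states which governs.

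**Step 6. Scale.** Section 1.2.1 gives, for the pooled combination trials, 13/359 = 3.6% with a Grade 4 event of any cause and 6/359 = 1.7% with a Grade 4 irAE. Both match the printed percentages. The protocol does not split either count by event type, so the share falling in the table's rows is unknown.

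**The case against.** The best defence is that the withdrawal rule is mandatory while the restart wording is permissive. A site that withdraws every patient with a drug-related Grade 4 event breaches nothing. That is correct. A reader might infer that no site can comply with all the texts, and the protocol does not support that. The conflict runs one way: a site that uses a restart permission breaches Section 3.3.4.1. A permission that cannot be used without a breach still needs correcting.

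A second defence reads the Grade 4 entry as a condition: withdraw if the patient can no longer be treated after such an event. The grammar allows it. But the entry just before already covers patients who cannot continue for medical reasons, including adverse events, so on that reading the Grade 4 entry adds nothing.

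Third, Appendix 10.4 calls its own guidance limited, and the specific might be taken to override the general. The protocol states no such hierarchy, and self-described limited guidance is a weak basis for overriding a mandatory criterion.

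Fourth, the Section 4.1.4 restart sentence concerns Part 1, where dose selection is complete. It also keeps a use for Grade 2 and Grade 3 DLTs if Grade 4 is excluded. This stands, so that limb is secondary. The Part 2 criterion in Section 4.1.4 leaves recovery to the investigator without a grade limit, but it is a necessary condition for continuing, not a permission to restart, and is not counted as a contradiction here.

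**Conclusion.** The point holds as an inconsistency between Section 3.3.4.1 and Appendix 10.4 for the listed Grade 4 irAEs in both parts, and between Section 3.3.4.1 and Section 4.1.4 for recovered Grade 4 DLTs in Part 1. It assumes that the investigator judges the event drug-related and that the Grade 4 entry is a withdrawal rule, not a redundant condition.

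The number of patients affected cannot be derived. It is tempting to apply the pooled rates to the 290 planned Part 2 patients (290 × 6/359 = 4.8; 290 × 13/359 = 10.5). That is not supported: Section 3.2 says the planned enrolment will not be reached, the 13 are all-cause, and both counts may include events on which the sections agree. Using the 44 patients still on treatment (44 × 6/359 = 0.7; 44 × 13/359 = 1.6) corrects only the denominator.

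Two further inferences should not be drawn. The protocol does not show that the classification of a re-treated patient as a deviation is undefined, because Section 7.3 assigns important deviations to the statistical analysis plan, which is not at hand. Nor does it show material distortion of the discontinuation endpoint, which is summarised descriptively and for which withdrawal reasons are recorded.

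**What to change.** Reconcile Section 3.3.4.1, the Part 1 restart text in Section 4.1.4 and the restart provisions of Appendix 10.4 so that they give one instruction for a drug-related Grade 4 adverse event. Add a sentence saying which section governs if they differ. Whether this is done by naming exceptions in the withdrawal list or by narrowing the restart permissions is a clinical decision for the sponsor, and this review takes no position on it.

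The cost is a few sentences in a protocol amendment and notice to the sites still treating patients. No new procedure, data item or analysis is needed.
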